The CaP TB model represents one potential way of improving the care of pediatric TB. However, it will be important to measure this model's effect on key service and clinical indicators related to pediatric TB in order to help guide future programming and resource prioritization. In order to describe the effect of the CaP TB model on these indicators, we plan a pre- and post-intervention evaluation in all project countries. We have chosen this pragmatic approach to allow us to compare the outcomes after we begin CaP TB implementation with the same indicators baseline (pre-implementation). This can help us define the effect of our specific project on the project evaluation indicators. As this is an evaluation of program implementation a randomized approach would not be feasible for both programmatic and financial reasons. We do recognize that secular trends may affect our outcomes, but we feel that the duration of the evaluation (over several years) and the large size and multi-country nature will help to mitigate that risk.

A. Pre-intervention Evaluation- Baseline assessment

In each country, a pre-intervention retrospective data collection will take place in a sub-set of project sites.

This data collection activity will:

1. Capture data that will answer the TB service indicators and clinical outcomes listed in the primary objectives.
2. Capture key data points that will be needed to estimate project targets

The main objectives of the CaP TB interventions are:

- to increase the number of children diagnosed with TB
- To increase the number of children who are started on and complete DS-TB treatment
- To increase the number of children who are started on and complete TB preventive therapy.

Key indicators that will be used to monitor project interventions and assess impact will therefore be:

- Number of pediatric cases diagnosed with active TB disease
- Number and proportion of pediatric DS-TB cases who achieve treatment success
- Number and proportion of pediatric patients started on preventive therapy of those who are eligible for preventive therapy
- Number and proportion of pediatric patients on preventive treatment who completed therapy

Data sources for these indicators during the pre-intervention phase are described in Table 1.

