In each site, trained data collectors will retrospectively extract data from appropriate registers, logs, and in some cases patient files, for a period of 12 months starting 6 or more months before the start date of data extraction. This time frame has been selected in order to allow to accurately measure indicators on treatment completion for both drug-sensitive TB treatment and preventive therapy (treatment lasts 6 months in both cases). In certain cases, the data sampling frame will start more than 6 months before the data extraction if CaP TB interventions had started during the sampling frame. Thus the sampling frame was chosen so that the end date of retrospective pre-intervention data abstraction would be before the start of any intervention to ensure that the baseline data was not affected by the early activities. For some indicators, baseline data will not be available in existing registers or logbooks. Data collectors will extract data from all pediatric entry points within the facility, including MNCH, HIV, nutrition and other relevant pediatric health care entry points. Only required variables will be abstracted and entered into the password-protected computers. Data with the patient date of birth (DOB), patient ID (if any), TB treatment ID and preventive treatment ID will be collected. The patient ID (if any), TB treatment ID and preventive treatment ID will all be encrypted before being uploaded into the CaP TB Database Entry Tool. DOB will be abstracted in order to facilitate tracking across registers if needed, as well as for data quality assurance purposes. This information will only be used to link registers. Only de-identified patient data will be abstracted into our global project

database. No other unique identifiers such as contact details of the children or their caregiver will be abstracted from the registers. Data from included pediatric patients will be extracted from the registers and recorded in the CapTB Baseline Data Abstraction form from where the data will be entered into a CaP TB Database Entry Tool (Excel-based and/or Web/mobile App-based) developed for pre-and post-intervention data , in a password protected computer and/or Android device (See Annex A: CapTB Information System).

The target population for the pre-intervention assessment is the records of any pediatric patient (0-14 years of age) who attend one of the sub-set of pilot sites in any of the 10 CaP TB countries who receive TB services. TB services include:

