To this aim, EGPAF will sub-contract University of Sheffield, key leader in childhood TB health economic modelling, to perform a cost-effectiveness analysis (CEA). The resulting effects estimates will be based on routinely collected project intervention country-level aggregates from key indicators describing the cascade of care, as well facility-level data for the comparison of the pre- and post- project intervention phase. All data to be used will have already been collected through TIPPI Pre-Intervention evaluation (described in section V, subsection A) and CaP-TB implementation evaluation (described in section V, subsection I).

Only aggregated clinical data will be shared with University of Sheffield and thus considered for the CEA analysis, as described below:

- i. Averaged monthly rates per site (including absolute numerator and denominator) of pediatric (children aged 0-14 years) TB notifications, DS-TB initiations, and PT initiations for a subset of sites for which both baseline and prospective data have already been collected (restricting to sites where data on both periods are available).
- ii. Country-aggregated project intervention numbers of: a) Children screened for TB, b) Children identified as presumptive TB, c) Children with presumptive TB tested with Xpert, d) Children diagnosed with TB, e) Children treated for DS-TB, f) All TB index cases for whom successful contact tracing has been done, g) Children started on TB Preventive Therapy (disaggregated by HIV and Contact investigation entry points), and h) Sites contributing to the country-level dataset.

All patient-level indicators mentioned in points i and ii above are included in Table 1. The cost-effectiveness analysis will use pre-intervention and project intervention data, with the potential for sub-analysis of shorter targeted period during the intervention phase.

The final cost-effectiveness analysis outcomes are expected to be reported by country, and individual countries will be identified to allow to use context-specific results to inform decision-making.

The costs will be estimated as follows:

- Core health services costs will be derived from published literature.
- CaP TB intervention costs will be estimated based on EGPAF CaP TB budgets and expenditure data from EGPAF's financial system.
- EGPAF country team staff will assist in allocating cost items to specific activities within the CaPTB cascade of service delivery.

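### The cost-effectiveness data list gives screening, presumptive, Xpert and contact-tracing volumes for the intervention phase only, so the comparator's upstream resource use must be assumed although baseline extraction is planned.

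*Combined protocol and SAP*

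**What the plan says.** Section VII.A sets the comparison: "The cost-effectiveness analysis will use pre-intervention and project intervention data". It then limits the clinical inputs: "Only aggregated clinical data will be shared with University of Sheffield and thus considered for the CEA analysis, as described below".

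Two items follow. Item (i) supplies site-level monthly averages, with the counts behind them, of pediatric "TB notifications, DS-TB initiations, and PT initiations for a subset of sites for which both baseline and prospective data have already been collected". Item (ii) supplies "Country-aggregated project intervention numbers of: a) Children screened for TB, b) Children identified as presumptive TB", then "c) Children with presumptive TB tested with Xpert", diagnoses, DS-TB treatment, "f) All TB index cases for whom successful contact tracing has been done", PT starts and the number of contributing sites.

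On cost, the section takes core health service costs from the literature and CaP TB costs from project budgets and expenditure. It names no source for the pre-intervention quantities of screening, presumptive assessment, Xpert testing or contact tracing.

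Section V.A gives as one purpose of the baseline data collection: "Capture data that will answer the TB service indicators and clinical outcomes listed in the primary objectives". These four steps are among those indicators (Section II.B), and Table 1 in Section VI names example pre-intervention sources for each. Section V.A also warns: "For some indicators, baseline data will not be available in existing registers or logbooks".

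**The concern.** An incremental cost-effectiveness ratio needs cost and effect for both arms of the comparison. Under the stated list the effect is net of baseline, but four service volumes are available only as gross intervention-phase totals. Some of that activity would have taken place under standard of care, and the list gives the modellers no way to observe how much.

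They would have to assume a baseline: zero, a figure scaled back from baseline notifications with intervention-phase ratios, or a published value. The plan does not say which. Scaling back assumes that CaP TB left unchanged the cascade proportions that it is meant to change (indicators a to e and k in Section II.B). The results are to be reported by country and to inform the allocation of funds (secondary objective c), and the error need not be the same in every country.

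**Working it through.** The documents state no incremental cost, unit cost, baseline volume or ratio, so there is no figure to reproduce. The check compares the two items and then illustrates the size under stated assumptions.

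**Step 1. What the list supplies for each period.**

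| Quantity | Pre-intervention | Intervention |
|---|---|---|
| TB notifications | item (i) | item (i) |
| DS-TB treatment starts | item (i) | items (i), (ii) |
| PT starts | item (i) | items (i), (ii) |
| Children screened | not listed | item (ii) |
| Presumptive TB | not listed | item (ii) |
| Tested with Xpert | not listed | item (ii) |
| Index cases traced | not listed | item (ii) |

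Three outputs are covered in both periods and four upstream volumes in one.

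**Step 2. Baseline volume set to zero.** Let b be the true baseline volume divided by the intervention volume, over equal time. The true increment is a fraction 1 − b of the intervention volume, so the overstatement is 1/(1 − b). The documents do not give b. Over an assumed range:

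- b = 0.10: 1/0.90 = 1.11-fold
- b = 0.25: 1/0.75 = 1.33-fold
- b = 0.50: 1/0.50 = 2.00-fold
- b = 0.75: 1/0.25 = 4.00-fold

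The value b = 0.50 corresponds to the expected two-fold rise in case detection (Section IX) with constant cascade ratios.

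**Step 3. Baseline back-calculated from intervention-phase ratios.** Section IX plans with 41 children screened per case found and a two-fold rise. Take 41 as the intervention-phase value, which is an assumption because Section IX uses it for target setting. Per baseline case, intervention screens are 2 × 41 = 82, imputed baseline screens are 41, and the imputed increment is 82 − 41 = 41. If baseline screening was really s per case (s assumed), the true increment is 82 − s:

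- s = 20.5: true 61.5, imputed/true = 0.67 (33% too low)
- s = 30: true 52, imputed/true = 0.79 (21% too low)
- s = 41: true 41, imputed/true = 1.00 (no error)
- s = 60: true 22, imputed/true = 1.86 (86% too high)

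**Step 4. Carry-over to incremental cost.** Let U be the intervention-phase cost of the four upstream services and P the CaP TB programme cost. Treatment and PT costs are left out because item (i) covers their starts in both periods. With a zero baseline, the ratio of computed to true cost is (P + U)/(P + U(1 − b)). For b from 0.10 to 0.75:

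- P = U: 2/1.90 to 2/1.25, overstated by 5% to 60%
- P = 3U: 4/3.90 to 4/3.25, overstated by 3% to 23%
- P = 10U: 11/10.90 to 11/10.25, overstated by 1% to 7%

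With the baseline imputed at b = 0.50, the ratio is (P + 0.5U)/(P + U(1 − b)). At P = U this gives 1.5/1.90 (−21%) at b = 0.10, no error at b = 0.50, and 1.5/1.25 (+20%) at b = 0.75. P and U are not in the documents, so these figures show only how the error behaves.

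**The case against.** The strongest reply is that an unstated method is not a demonstrated error. The list restricts the clinical data passed to the modellers but does not bar published inputs, and the section already takes core service costs from the literature. CaP TB costs come from project accounts and need no baseline volume. Nothing in the documents proposes a zero baseline, and Step 3 includes a case with no error. This stands: a reader might infer that incremental cost is biased, but the documents support only a risk of bias.

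A reader might also infer that the comparator has no resource use at all. That is wrong, because item (i) supplies baseline treatment and PT starts. For the same reason, the expected four-fold rise in preventive therapy is not an example of the gap. The denominators in item (i) do not close it either: they belong to rates of three downstream outputs, and nothing defines them as counts screened, tested or traced.

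A further reply is that the baseline data may be poor. Section V.A expects gaps, Table 1 is offered only as an example, and it lists contact-tracing records conditionally. Subtracting logbook counts from counts made with the new project tools would also mix real change with better recording. This is a fair limit on how precise the fix can be. It calls for ranges, but it is not a reason to withhold the volumes that are recorded.

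**Conclusion.** The point holds in this form: the comparator has treatment and PT starts but no observed upstream screening, testing or tracing volumes, and the stated list leaves out baseline volumes that the evaluation itself plans to extract. Incremental cost is therefore at risk of bias in that component. The bias would be upward with a zero baseline (2-fold on upstream volume if half was pre-existing), and in either direction or nil with back-calculation.

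The sizes rest on assumed baseline shares, on 41 screens per case holding in the intervention phase, and on assumed ratios of programme to service cost. The effect on the final ratio cannot be derived from the documents. If programme cost dominates, it could be small. Because this concerns a secondary objective and the data are already planned, it is a cheap improvement.

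**What to change.** In Section VII.A, extend item (i) with baseline and intervention monthly numbers of children screened, presumptive and Xpert-tested, and of index cases traced, at the sites with both periods, where registers record them. Base the incremental upstream volumes on the difference between periods at those sites, which are also the sites that item (i) uses for notifications and treatment starts.

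Mark a step that the baseline registers do not hold as not recorded, never as zero. For those steps, report a sensitivity range from zero baseline volume to baseline at the intervention-phase cascade ratio, extended to higher baseline use per case, because Step 3 shows that the ratio-based value is not an upper limit. Apply the range also where baseline logbooks are likely to under-record compared with the project tools; there the recorded count can replace zero as the lower end.

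The cost is a few more aggregated columns in the data transfer and one sensitivity analysis, with no new data collection. The downside is that gaps in some countries and differences in recording between periods will leave some results as ranges.

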 - m. Number and proportion of screened negative pediatric contacts eligible for preventive therapy
 - n. Number and proportion of pediatric patients started on preventive therapy of those who are eligible for preventive therapy
 - o. Number and proportion of pediatric patients on preventive treatment who completed therapy

2. Secondary Objectives

- a. To determine the effect of the CaP TB project on the above TB service indicators and clinical outcomes compared to baseline (standard of care) in a subset of project sites.
- b. Utilize the evidence generated from this program evaluation to support strategic recommendations to improve pediatric TB care.

- c. Utilize clinical aggregated data generated by this study to inform cost-effectiveness analysis of pediatric TB interventions implemented by CaP TB project that can contribute informing childhood TB planning and strategic allocation of financial resources
- d. Utilize evidence generated from this program to assess the impact of measures enforced to control the COVID -19 pandemic on accessibility and availability of pediatric TB services

III. Expected Outcomes of the Study

The main expected outcome of CaP TB project is to reduce morbidity and mortality associated with pediatric TB^{xxx} by reducing the pediatric TB diagnostic and treatment gap, increasing coverage of quality assured TB treatments, as well as scale up of TB preventive therapy through innovative models of care for pediatric TB that focus on integration and decentralization. We expect that this program evaluation will document a positive impact of the CaP TB model, with estimated two-fold increase in case detection and four-fold increase in pediatric patients started on TB preventive therapy based on project target estimates. The evaluation of the CaP TB project will allow for dissemination of the results and further uptake of proven models by other countries.

IV. Study Design

We are planning a pre-/post-project (quasi experimental) intervention evaluation. The population will include all pediatric patients (0-14 years of age) who present to a CaP TB project site in any of the 10 countries and receive TB services (including screening, diagnosis and treatment for active TB, and provision of TB preventive therapy).

A. Methodology

[figure not shown]
1. Description of the CaP TB Project

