Location of activity	10-20 purposively selected pilot sites in each country, for a total of up to 200 sites across all ten countries. Sites will be selected based on geography (urban vs rural) and health facility level. We estimate that 12 months of data will be sufficient to appropriately assess the indicators from the primary objectives under standard of care conditions. The overall sample size in each country and per facility sample size will vary greatly by facility level, pediatric population density and indicator. However, we estimate that we will collect data for at least 5 children with presumptive TB in each clinic.	Up to 70 sites in each country for a total of up to 700 sites across all ten countries.
Timing	15-20 CaP TB pilot sites in each country	All CaP TB sites across 10 countries (up to 700 sites)
Method	Retrospective data collection will occur upon site selection. It is estimated that the retrospective data collection for all sample project sites in a given country will take six to ten weeks.	Data collection will begin when each site begins implementation of CaP TB and will go on through the end of the project
	Data abstraction of TB registers, HIV registers, PMTCT registers and other relevant logbooks	Data abstraction from clinic attendees registers, Pediatric TB Intensified Case Finding Screening Tool, CaP TB Pediatric TB Form, TB treatment register, TB preventive therapy register and other TB registers and logbooks as needed

Informed Consent documents	Informed consent waiver to be requested	Informed consent waiver to be requested
Data collection tool	Baseline data abstraction tool	Pediatric TB Intensified Case Finding Screening Data Abstraction Tool and CaP TB Database Entry Tool

IX. Data Management and Statistical Analysis

Quantitative de-identifiable data extracted from the source documents will be coded and entered directly into a database that will be designed specifically for the project and stored on a secure cloud server. Data will be aggregated in the database and entered into an electronic dashboard that will demonstrate the data standardized to project indicators and data elements. Frequencies will be calculated for each response and descriptive statistics will be calculated.

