Project data sample size: As this is a project evaluation, no specific sample size has been calculated. However, we estimate that the project will increase case detection by 2-fold and result in an additional 16,471 pediatric TB cases being treated.^{xxxix} This is based on an assessment of the number of children we project to screen (both HIV positive and HIV negative) in our project sites throughout the project. From the literature, we estimate that approximate Number Needed to Screen (NNS) to identify 1 TB case is 41 children. Assume that Number Needed to Screen (NNS) to identify 1 TB case is 41 (estimated NNS when symptom based screening is the only primary screening done)^{xl, xli}. Preventive treatment coverage is estimated to increase by four-fold, with an additional 52,317 children to be initiated on preventive therapy. This is based on the estimated number of child TB contacts we will identify through contact tracing plus HIV-infected children who qualify for preventative treatment.

To compare pre- and post-intervention outcomes, we will use either the ratio of the two proportions (relative risk) or the difference between the two proportions (risk difference). We will use Z-tests to assess the statistical significance of the estimated effect of CaP TB.

For measuring turn-around-time (TAT) between when a child is identified as a presumptive TB case and when the child is diagnosed with TB and the TAT between when a child is diagnosed as a presumptive TB case and when the child initiates TB treatment, if the TATs are approximately normally distributed, we will use the paired t-test to assess for statistical significance, otherwise we will use the Wilcoxon rank sum non-parametric test.

A. Quality Assurance

All data collectors will be trained in quantitative data collection by EGPAF staff. Prior to training, all data sources, abstraction and collection tools and procedures will be reviewed and tested. The HQ EGPAF team will provide on-going support to in-country teams throughout program implementation and all data collection activities.

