The Elizabeth Glaser Pediatric AIDS Foundation is responsible for protocol development and other study documents, overall conduct and management and the scientific integrity of the study. EGPAF will also serve as the liaison for communication and coordination with ethical review boards, the Ministry of Health in each project country, UNITAID and other stakeholders. The overall project management, including all aspects of the intervention, will be led by [name], Senior Director of Innovations at EGPAF. The day-to-day management of the project's implementation will be managed by [name], Project Director of CaP TB and [name], Technical Director of CaP TB. The data and program evaluation will be managed by [name], Strategic Information and Evaluation lead for the CaP TB project. [name] is a Senior Biostatistician at EGPAF and will be responsible for developing of the statistical analysis plan, review and analysis of data, and contribute to the write up of study findings. Each project country has a country implementation manager who will be responsible for the day-to-day management of activities, and a Senior Strategic Information and Evaluation officer who will manage day-to-day responsibilities for the project evaluation.

[figure not shown]
XV. Annex A: CaP TB Information System

The CaP TB Database Entry Tool will abstract the information contained on, and matching the 2nd page (blinded for patient personal details) of the CaP TB Pediatric TB Form. We will use a combination of web/mobile App or Excel entry templates, both directly feeding into a unique database. Below are example of data flow in both models. A generic Excel based template of the CaP TB Database Entry Tool is provided as part of this protocol submission. As the CaP TB Pediatric TB Form will be adapted by countries to align with country-specific requirements, the CaP TB Database Entry Tool will also be consequently adapted to a perfect match.

Data System using MS Excel as Data Collection Tool

Data System using Power Apps as Data Collection Tool

References

- ^I TB Facts. <http://www.tbfacts.org/tb-children/#sthash.F7e8OM9G.dpuf>
- ^{II} Seddon et al 2015_Counting children with TB_ IJTLD
- ^{III} Global tuberculosis report 2017. Geneva: World Health Organization; 2017. Licence: CC BY-NC- SA 3.0 IGO.
- ^{IV} WHO Global TB report 2015

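### The pre/post Z-tests on proportions ignore site and country, although CaP TB is delivered by facility and the baseline sites are observed in both periods, so the p-values are not valid as written

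*Combined protocol and SAP*

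**What the plan says.** Section IX compares the two periods by the ratio or the difference of two proportions and then states: "We will use Z-tests to assess the statistical significance of the estimated effect of CaP TB". No other test is given for proportions. The section does not say how the standard error is obtained, and it mentions neither site nor country.

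The design is described elsewhere:

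- Secondary objective (a) in Section II.B.2 is the effect of CaP TB "compared to baseline (standard of care) in a subset of project sites".
- Table 3 (Section VIII.A) puts the baseline in "10-20 purposively selected pilot sites in each country, for a total of up to 200 sites across all ten countries". Post-intervention data come from all project sites, up to 700, which include the pilot sites.
- On volume, Table 3 says: "The overall sample size in each country and per facility sample size will vary greatly by facility level, pediatric population density and indicator". The only number is a floor: "However, we estimate that we will collect data for at least 5 children with presumptive TB in each clinic".
- Section IV.A.2 describes training, supervision, TB champions and feedback given to facilities, in packages that differ by country.
- Section VII.A limits per-site rates to matched sites ("restricting to sites where data on both periods are available"), but only for the cost-effectiveness data.
- Section XIV says that the senior biostatistician "will be responsible for developing of the statistical analysis plan, review and analysis of data". Apart from the secondary analyses outlined in Section VII, Section IX is the only analysis text in the documents.

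**The concern.** A two-proportion Z-test treats every child as an independent observation and the two periods as independent samples. Neither holds here. Children at one facility share staff, case mix, diagnostics and record keeping, so their outcomes are correlated. The baseline facilities appear in both periods, so the two proportions are correlated as well.

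The two departures act in opposite directions. Within-site correlation makes the plain standard error too small; positive correlation between a site's two periods makes it too large. The net result depends on how far site levels drift between periods, on volume per site, and on whether the same sites enter both sides.

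At stake is secondary objective (a), for which this is the only stated test of proportions. Any interval built from the same standard error is affected too. The indicators most exposed are those for which no large change is forecast. Section V.A lists "Number and proportion of pediatric DS-TB cases who achieve treatment success" and preventive-therapy completion among the key indicators, and no expected size of change is given for either. The point concerns proportions only; counts, such as the number of cases diagnosed, need their own method.

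**Working it through.** The plan gives no sample size, power, alpha or ICC, so it has no figure of its own to reproduce. The check asks what error rate a nominal 5% Z-test would have.

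**Inputs from the documents.** Up to 200 baseline sites and up to 700 post-intervention sites; at least 5 presumptive cases per clinic.

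**Assumptions.** Two-sided alpha 5%; ICC 0.05-0.20; CAC (correlation of a site's level between periods) 0.5-0.8, with 1.0 as the limiting case; m = 5, 20 or 50 children per site per period.

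**1. Same sites in both periods, equal volumes**

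Design effect: DE = 1 + (m − 1)·ICC − m·ICC·CAC

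True error = 2·[1 − Φ(1.96/√DE)]

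Example with m = 20, ICC 0.20, CAC 0.5: DE = 1 + 3.8 − 2.0 = 2.80, and the error is 2·[1 − Φ(1.96/1.673)] = 24.1%.

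| m | DE, CAC 0.5-0.8 | True error, CAC 0.5-0.8 | True error, CAC 1.0 |
|---|---|---|---|
| 5 | 1.00-1.30 | 5.0-8.6% | 2.8-4.4% |
| 20 | 1.15-2.80 | 6.8-24.1% | 2.8-4.4% |
| 50 | 1.45-5.80 | 10.4-41.6% | 2.8-4.4% |

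At CAC 1.0, DE = 1 − ICC (0.80-0.95) at every m. At m = 5 and CAC 0.8 the two terms cancel and the test is exactly nominal.

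**2. All 700 post-intervention sites against the 200 baseline sites**

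Section IX does not exclude this comparison. With K sites and m children per site in each period:

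DE = [(1 + (m₀ − 1)·ICC)/(K₀m₀) + (1 + (m₁ − 1)·ICC)/(K₁m₁) − 2·ICC·CAC/K₁] / [1/(K₀m₀) + 1/(K₁m₁)]

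With K₀ = 200, K₁ = 700, m = 50 and ICC 0.05, DE is 2.34, 2.56 and 2.89 at CAC 1.0, 0.8 and 0.5. The error is 20.0%, 22.1% and 24.9%. Here even perfectly stable sites do not protect the test.

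**3. Simulation with no true effect**

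Settings: 4,000 runs per setting; 150 matched sites (15 × 10 countries); typical-site proportion 0.1 to 0.7; logit-scale site SD 0.7 and site-by-period SD 0.3 (implied ICC 0.06-0.12, CAC 0.83-0.84); post volume three times baseline.

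| Mean baseline m | Z-test, equal sites | Z-test, unequal sites (cv 0.7) |
|---|---|---|
| 5 | 4.6-5.2% | 6.6-7.2% |
| 20 | 7.9-9.6% | 10.4-15.4% |
| 50 | 13.2-18.2% | 18.0-25.4% |

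In the same runs, the same risk difference with site-clustered robust errors rejected in 4.1-5.8%, and a site-paired t-test in 4.1-5.4%.

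**4. Effect on conclusions (150 sites, equal volumes, ICC 0.05-0.20, CAC 0.5-0.8)**

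- Assumed change from 80% to 83%, m = 20, so 3,000 children per period. Plain Z = 0.03/√(2·0.815·0.185/3000) = 2.99, p = 0.003. Dividing by √1.15 = 1.07 gives Z = 2.79, p = 0.005; dividing by √2.80 = 1.67 gives Z = 1.79, p = 0.07.
- Assumed change from 10% to 20%, m from 5 to 50. Corrected Z is lowest at m = 5, ICC 0.20, CAC 0.5: 5.42/√1.30 = 4.76. The result stays significant throughout.

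**The case against.** The strongest reply is that Section IX does not specify the standard error. A Wald statistic from a cluster-robust model is also a Z-test, and Section XIV promises a statistical analysis plan that could supply the detail. This is possible. But the text describes only two aggregate proportions and names no adjustment, although the same section does name a paired test for turnaround times. Nothing in it obliges the later plan to handle clustering.

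The second reply is that the size rests on assumptions, and this stands:

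- The 41.6% needs ICC 0.20, CAC 0.5 and m = 50 together.
- At ICC 0.01 and CAC 0.5-0.8 the error is only about 5.3-6.0% at m = 20 and 6.0-7.8% at m = 50.
- For treatment success, m = 20 may be high. The 16,471 additional cases in Section IX, spread over 700 sites, are about 23.5 per site for the whole project. If that represents a doubling over an assumed 2-3 years, baseline is roughly 8-12 cases per site-year. At m = 8-12, ICC 0.05-0.20 and CAC 0.5-0.8, the error is 5.3-16.6%. Pilot sites may be larger than average.

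It is also fair that the primary objective is descriptive, that the forecast two-fold rise is a case count rather than a proportion, and that clustered errors do nothing about the secular trends acknowledged in Section V. These points limit the consequences. They do not make the test valid, because its error rate still depends on quantities that the plan neither states nor uses.

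**Conclusion.** The concern holds: followed as written, the Z-test does not control its error rate for secondary objective (a). The direction and size of the error cannot be fixed from the documents. With matched sites, equal volumes and perfectly stable site levels the test is mildly conservative, and at the floor of 5 children per site the distortion is small. It becomes anti-conservative as site levels drift, volumes rise or become unequal, or all project sites are set against the baseline subset. Under the stated assumptions, a nominal 5% then becomes roughly 7-24% at 20 children per site. Large effects would probably survive. A modest change of a few percentage points could be reported as clearly significant when a valid analysis would leave it uncertain. This should be fixed before analysis, but it does not undermine the descriptive primary objective.

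**What to change.** Replace the Z-test sentence in Section IX with text to this effect:

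*Pre/post comparisons of proportions use only sites with data in both periods. Relative risks and risk differences with 95% confidence intervals are estimated by GEE (log or identity link, or logit link with marginal standardisation), with period and country as fixed effects and robust standard errors clustered on site. Single-country estimates, which rest on 10-20 sites, use a small-sample corrected standard error. Site-level paired differences stratified by country are reported as a sensitivity analysis; they estimate a site-average effect, not a child-weighted one.*

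A mixed model with random site and site-by-period effects and marginal standardisation is an acceptable alternative. The essential part is matched sites with site-clustered or site-paired errors; the choice of link and model is secondary. Alpha and sidedness should be stated at the same time.

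The cost is a change of wording and modest extra analysis. Data are already held by site and country, so nothing new is collected. Confidence intervals will usually be wider.
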